#### **(4) Measures of Food Literacy**

- *Healthy Food Knowledge.* This pictorial-based knowledge assessment will be based on the content of the food literacy curriculum. We will provide participants with pictures of 25 different foods and ask them to classify them by the correct food group (e.g., an apple belongs to the fruit group) (5 foods for each of the 5 food groups). The participants will be shown three pictures of whole grain foods in their packaging and three pictures of non-whole grain foods in their packaging and asked to indicate whether or not each food is a whole grain. We will do qualitative probes to understand why/how the participant selected their response. Likewise, participants will be presented with a bottle of water and a bottle of soda and asked which has less sugar. This will be repeated with water and a sports drink. Qualitative probes will query the reason for the answer. Participants will be shown 2 plates of food: (1) chicken, rice, and broccoli; and (2) chicken, rice, and bread, and asked which is the healthier meal. Again, we will query why they made the choice they did. This question will be repeated with 2 other plates of food: (1) salmon, quinoa, and asparagus; and (2) salmon, quinoa, and bread. This assessment will be administered remotely via Zoom.
- *Healthy Eating Behavior.*
  - Changes in adolescent dietary behavior will be obtained by parent proxy from modifications of the dietary assessment questions as part of the Youth Risk Behavioral Surveillance Survey (YRBSS). There are 9 questions related to dietary intake that align with our lessons around fruit/vegetables and added sugars. Parents will be asked to answer questions on the YRBSS about their adolescents’

intake of fruits and vegetables and sugar-sweetened beverages over the past week. A proxy measure of food intake is most appropriate given the wide range of cognitive abilities we expect among participants and difficulty with accurate recall. Parents will complete the 9 questions for their adolescent at baseline and post-intervention virtually over Zoom, to yield a summary dietary behavior score.

- We will also administer a modified food frequency questionnaire (FFQ) that we have developed for other studies that contains lists of foods organized by food group. This will be administered virtually over Zoom. Parents will be asked to indicate which foods their teen eats, which foods their teen will not eat, and whether any of the foods are never served to the teen. There is also a single question that asks parents to indicate how willing their teen is to try new foods. The FFQ will allow us to assess whether the teen's willingness to try new foods changes as a result of the intervention and whether there is an increase in the proportion of foods of the total that they consume post-intervention.

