- If the adolescent meets criteria for ID, we will then review the online Assent Form which has been constructed as a “social story” which provides visual supports/information as the RA describes the program to the adolescent. We have chosen to acquire assent after the IQ test so that the participant does not potentially become interested/excited about the program only to be informed of the inability to participate, should they not meet inclusion criteria.
- Upon completing the assent we will administer the baseline questionnaires described above to both the adolescent and parent, including the Food Knowledge Test. We will provide the option to have these take place at a separate, second enrollment session that will be virtual. We will also provide the parent with the option to complete the parent questionnaires independently, offline, and offer additional Zoom calls in the event they have any questions or are unable to complete the forms on their own.

At the last enrollment session that will again take place over Zoom, the Test of Gross Motor Development-Third Edition (TGMD-3) measures will be administered by a trained professional with the help of the participant’s parent.

One week prior to the start of the intervention, we will hold parent orientation Zoom calls to orient parents to the session structure, at-home components, and what their week-to-week responsibilities will be.

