## **12. DATA AND SPECIMEN BANKING\* N/A**

### **13. Data Analysis and Management\***

All data will be double entered and linked by a common identification number across data sources. We will minimize missing data through careful checking of all surveys and data forms at the time of completion. Baseline characteristics of participants who drop out will be compared to those who complete the study.

Analyses for Specific Aim #1. The process measures of feasibility will assess attendance, degree of participant enjoyment, and participant and parental satisfaction based the aforementioned surveys. These measures will be summarized as means and proportions, with corresponding 95% confidence intervals, and compared across the two waves. If there are no important differences, we will pool across waves. We will use the 6-week and 12-week measures to assess if engagement builds, sustains or declines over the intervention period. We will also examine study completion and attendance by wave.

Analyses for Specific Aim #2a. To assess if the intervention increases aspects of physical literacy including movement competence (ability), confidence, and desire to participate in physical activity, we will conduct 1-sample paired t-tests for change (against the null hypothesis of a change of zero) in separate tests for TGMD-3 scores, PSI-VSF-ID physical self-concept, and CSAPPA score. We will construct 95% confidence intervals around the measure of change separately for boys and girls, and pool them if we discern no important differences by sex. If, based on Aim #1, we believe there were important implementation differences between the two waves, we will analyze them separately, acknowledging our power will be more limited.

Analyses for Specific Aim #2b. Analyses to assess if the intervention increases elements of food literacy (i.e., knowledge and skills) for promoting intake of fruits and vegetables and for decreasing intake of high energy low nutrient dense snack foods will proceed as for Aim #2a. We will use a 1-sample (paired) t-test to test Food Knowledge, Food Skill Master, and Dietary Behavior scores. We will construct 95% confidence intervals around the change separately for boys and girls, pooling them if we discern no important difference by sex. If, based on Aim #1, we believe that there were important implementation differences across the two waves, we will analyze them separately, acknowledging our power will be more limited.

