## **26. CONFIDENTIALITY**

Confidentiality of participants will be protected in several ways. All participants will receive an identifying number for coding and analyzing data. Informed consent and identifying code numbers will be kept in a separate file from completed data questionnaires. Data will be reported

in group format only; if any need should arise to report individual data, it will be accessible only to the research team and identifying information will not be reported that might allow the individual's identity to be discerned.

Data will consist of a recording of and performance on the TGMD-3 test, completion of questionnaires by participants and parents, and recording of the virtual intervention sessions on Zoom. All video recordings will be stored in a password-protected, HIPAA-compliant, cloud-based server. Questionnaires will be administered by paper or electronically using REDCap. All paper-based data will be kept in a locked file cabinet and will be accessible only to the research team. Individual names and identifying characteristics will not be shared with others outside of the research team. Requests or discussions regarding participation in the study will be made by letter or phone calls in a separate, private room.

Subjects will be provided with an Amazon Fire Tablet for use during the study. No identifying information will be stored on these devices during the duration of the study however we will allow participants to keep these devices after the intervention at which point they can choose to disclose personal information. The privacy statement for the Amazon Fire tablets can be found here: <https://www.amazon.com/gp/help/customer/display.html?>

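### The mode of the parent diet questionnaires is not held constant between baseline and post-intervention, so a mode effect could enter the estimated change in diet

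*Combined protocol and SAP*

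**What the plan says.** Three places in the combined protocol and SAP describe how parents answer the diet questionnaires.

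- **Section 10, Measures of Food Literacy.** For the nine YRBSS items: "Parents will complete the 9 questions for their adolescent at baseline and post-intervention virtually over Zoom". For the FFQ: "This will be administered virtually over Zoom". The FFQ sentence names no visit, but the instrument is meant to show change, namely "whether there is an increase in the proportion of foods of the total that they consume post-intervention".
- **Section 11, Participant Screening & Enrollment.** "Upon completing the assent we will administer the baseline questionnaires described above to both the adolescent and parent". This takes in both parent diet instruments. The same paragraph continues: "We will also provide the parent with the option to complete the parent questionnaires independently, offline, and offer additional Zoom calls".
- **Section 26, Confidentiality.** "Questionnaires will be administered by paper or electronically using REDCap". No visit or instrument is named.

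For the analysis, Section 13 says: "We will use a 1-sample (paired) t-test to test Food Knowledge, Food Skill Master, and Dietary Behavior scores". The study has one arm.

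**The concern.** The sections do not agree on mode. A parent following them as written could answer offline at baseline and over Zoom 12 weeks later. The plan does not require the same mode at both visits, does not record the mode, and has no term for it in the analysis.

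In a two-arm trial, a mode change common to both arms would largely cancel in the between-arm comparison. Here the estimate is the mean within-person change, tested against zero. If the same diet is reported differently in the two modes, the difference among parents who switch is added to that mean and cannot be told apart from a real change in eating. If mode is not recorded when the data are collected, it may not be recoverable at analysis. The Aim 2 results are meant to inform a larger controlled study, so an avoidable source of error in one of the food-literacy outcomes is worth removing.

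**Working it through.** **Step 1: the text by visit**

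| Instrument | Baseline | Post-intervention |
|---|---|---|
| YRBSS diet items | Zoom (Section 10); offline at the parent's choice (Section 11); paper or REDCap (Section 26) | Zoom (Section 10); paper or REDCap (Section 26) |
| FFQ | Zoom, visit not named (Section 10); offline at the parent's choice (Section 11); paper or REDCap (Section 26) | Zoom, visit not named (Section 10); paper or REDCap (Section 26) |

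The offline option is written only into the enrollment procedures. No section rules out a different mode at the two visits.

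**Step 2: how a mode effect enters the estimate**

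Let f be the share of completers who switch mode and m the mean effect of switching on the reported score, in SDs of the change score. With no true change in diet, the expected mean change is b = f × m. For example, f = 0.5 and m = 0.3 give b = 0.15 SD. If every parent keeps one mode, f = 0 and b = 0.

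**Step 3: illustrative size**

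The plan gives no figure that depends on mode, so there is none to reproduce. The inputs are:

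- Enrollment of 30 (Section 25) and a 10% dropout allowance (Section 24): 30 × 0.90 = 27 completers.
- Alpha of 0.05, which Section 13 states for the sample-size calculation. Sidedness is not stated; two-sided is assumed.
- f and m are not in the documents and are assumed.

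The rejection rate with no true change is P(|T| > t), where T is noncentral t with n − 1 degrees of freedom and noncentrality b × √n. For n = 27, there are 26 degrees of freedom and t = 2.056. For b = 0.15 the noncentrality is 0.15 × √27 = 0.779.

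| Mean bias b (SD of change) | n = 27 | n = 30 |
|---|---|---|
| 0 | 5.0% | 5.0% |
| 0.05 | 5.7% | 5.8% |
| 0.10 | 7.9% | 8.3% |
| 0.15 | 11.7% | 12.5% |

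**Step 4: dependence on uptake**

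The formula treats the bias as a uniform shift. When only some parents switch, the mixture slightly widens the spread of the change scores. A simulation of 100,000 trials at n = 27 allows for this:

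| Share switching | m = 0.2 | m = 0.3 | m = 0.5 |
|---|---|---|---|
| 25% | 5.6% | 6.4% | 9.3% |
| 50% | 8.0% | 11.5% | 23.6% |

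With m = 0 the rate is 5% whatever the uptake. With low uptake or a small mode effect the inflation is slight. Section 13 also builds intervals for boys and girls separately; at n = 15 a bias of 0.15 SD gives 8.4%, because the smaller sample has less power to detect a bias of that size.

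**The case against.** The strongest reply is that the switch is inferred from silence. Section 11 covers screening and enrollment and would not be expected to describe the post-intervention visit, for which there is no procedures section. Section 26 can be read as allowing self-completion at either visit. This stands in part: a Zoom-only second visit is not established. It does not remove the point, because that reading leaves mode less controlled, not more.

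A reader might infer that families move from a private report to an interview with study staff, and hence that post-test answers will look too favourable. The documents do not support this. Section 10 says parents complete the diet items over Zoom; it does not say that staff read the items aloud or hear the answers, whereas it does specify verbal administration for the adolescent activity questionnaires. No section gives the direction of any mode effect. Parents also attend the nutrition sessions with their child, so a pull towards favourable answers may exist in any mode.

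A reader might also apply the false-positive rates to the FFQ. Section 13 lists no FFQ test, so they do not apply there, although a change of mode could still affect the FFQ's descriptive change.

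Finally, this is a pilot whose first aim is feasibility, its efficacy claims are preliminary, no progression rule rests on the diet score, and flexibility for families is defensible. All of this stands and limits the severity.

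**Conclusion.** The inconsistency is real and is not resolved elsewhere in the document. As written, mode can differ between a parent's two reports, and the single-arm paired test cannot separate a mode effect from a change in diet.

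The size is unknown. With 27 completers, a two-sided 5% test and no true change, assumed mean biases of 0.05 to 0.15 SD give error rates of about 5.7% to 11.7% for the Dietary Behavior score. These rates rest wholly on assumed uptake and mode effects; they show sensitivity and do not predict what will happen. A bias in the unfavourable direction would instead hide a real improvement. Minor to moderate severity for a pilot.

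**What to change.** 1. Reconcile Sections 10, 11 and 26 so that they give one account of how parents complete the YRBSS items and the FFQ at each visit.
2. Have each parent complete both instruments after the intervention in the mode used at baseline, with the same parent responding where possible. The plan does not name the respondent, and a change of respondent would act on the change score in the same way as a change of mode.
3. Record mode and respondent at each visit in REDCap.
4. In Section 13, add a sensitivity analysis of the Dietary Behavior change limited to families with the same mode at both visits, and report how many switched.

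The cost is about a sentence in each section, two REDCap fields and one extra analysis. Parents keep their choice at baseline but have slightly less flexibility at post-test. The same-mode subset will be smaller and less precise. The change removes one avoidable source of bias; it does not remove favourable reporting that comes from having attended the sessions.

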## **11. PROCEDURES INVOLVED\***

### **Overview**

The intervention will be conducted remotely using Zoom.

We will recruit 15 male and 15 female adolescents with ID ages 12-16. To establish the presence of ID (IQ  $\leq 75$ ), the Kaufman Brief Intelligence Test, 2nd ed. (KBIT-2) will be used to determine IQ score and the Vineland Adaptive Behavior Scales-III (VABS-III) will be used to assess adaptive functioning. Because the etiology of ID is variable, we expect the sample will include adolescents with various syndromes (e.g., Down syndrome, Fragile X, Williams syndrome) as well as those with autism and ID of unknown etiology. The KBIT-2 will be administered remotely via Zoom by a trained research assistant per the protocol developed by the test developer Pearson Assessments. The VABS-III will be completed online via the online administration program developed by Pearson.

### **Participant Screening & Enrollment**

Parents will be phone-screened for their adolescent child's eligibility via a or Zoom phone interview. The procedures for adolescents who meet the inclusion criteria on the phone screen will be as follows:

- In order to determine the key inclusion criteria of the adolescent having an intellectual disability, parents will first be asked to complete an online version of the Vineland Adaptive Behavioral Scales-III which enables us to ascertain the adolescent's adaptive behavior. They must receive a score of 75 or less to be eligible. The VABS-III can be done at the time of the screening call with the RA or at another time of the parent's choosing. The RA can offer to be present during the time that the parent is completing this questionnaire in the event they have questions, but this is not necessary or a requirement. Will give parents the option of how/when they wish to complete the VABS-III. Pearson Assessments provides an online platform for parents to complete the VABS-III. The platform will then automatically score the questionnaire. Pearson will not be provided with or have access to any identifying information about the parent or child.

- If the VABS-III yields a score of 75 or less, we will then schedule a Zoom meeting for the adolescent and their parent. The RA will meet briefly with the adolescent to introduce himself to the adolescent and briefly describe the program. If the adolescent indicates an interest and willingness to proceed, the RA will administer the Kaufman Brief Intelligence Test – 2 (KBIT-2) to confirm an IQ of 75 or less, which is required for classifying the adolescent as having an intellectual disability (ID). If the KBIT-2 yields a score of 75 or lower, the rest of the enrollment meeting will proceed as described below. If the score is 76 or higher, the adolescent and parent will be told that the adolescent does not meet our screening criteria for ID. The KBIT-2 will be administered to the adolescent over Zoom, according to remote administration guidelines published by Pearson.
- If the adolescent meets criteria for ID, we will then review the online Assent Form which has been constructed as a “social story” which provides visual supports/information as the RA describes the program to the adolescent. We have chosen to acquire assent after the IQ test so that the participant does not potentially become interested/excited about the program only to be informed of the inability to participate, should they not meet inclusion criteria.
- Upon completing the assent we will administer the baseline questionnaires described above to both the adolescent and parent, including the Food Knowledge Test. We will provide the option to have these take place at a separate, second enrollment session that will be virtual. We will also provide the parent with the option to complete the parent questionnaires independently, offline, and offer additional Zoom calls in the event they have any questions or are unable to complete the forms on their own.

At the last enrollment session that will again take place over Zoom, the Test of Gross Motor Development-Third Edition (TGMD-3) measures will be administered by a trained professional with the help of the participant’s parent.

One week prior to the start of the intervention, we will hold parent orientation Zoom calls to orient parents to the session structure, at-home components, and what their week-to-week responsibilities will be.

### **Physical Literacy & Food Literacy Intervention.**

The 12-week intervention is designed to expose adolescents with ID to a variety of sports skills and healthy eating concepts to equip them with skills and confidence to participate in physical activities and make healthy food choices. The proposed sport sampling and healthy eating program will follow a protocol that can be adapted to meet the needs of a diverse group of adolescents with ID. Sessions will be held weekly for an hour and fifteen minutes. One cohort will meet Thursday evenings, the second cohort will meet Saturday mornings, and the third cohort will meet at a day/time that is to be determined based on the input of participating families on other days/times that would have worked for their schedules. 35 minutes will be dedicated to sport activities followed by 35 minutes dedicated to the curriculum on healthy eating with a 5 minute break in between. All sessions will be recorded to be coded as data at a later time by graduate students.

Sport Skills Sampling. The sport skills program will be delivered remotely with modifications that promote engagement in activities at home. The program will be organized by general sport

types/categories that are familiar to youth with ID and share key underlying motor skills. Four (4) weeks will be dedicated to each sport type including: striking sports, running and jumping sports, and ball sports. This classification of sport types (which are not mutually exclusive) will allow us to focus on fundamental locomotor and object control skills that are building blocks for a variety of sports, games, and physical activities, and that youth with ID can enjoy and practice on their own or with others. The selection of sport types is based on those that are popular for the age group, readily available to youth with ID in schools/communities (e.g., YMCAs), and part of Special Olympics. These include: baseball (striking sport); tennis (striking sport); basketball (ball sport); soccer (ball sport); track and field (running and jumping sport); floor hockey (striking sport); volleyball (running and jumping sport); and gymnastics (running and jumping sport). Available physical literacy resources, materials, and curricula have guided the development of the sport skills curriculum and lessons. A “sports kit” will be delivered to each participant containing all the equipment that they will need to engage in the sports activities during each session (e.g., soft foam balls, cones, targets, paddles, jump rope, agility ladder). The items in the kit will all be usable in an indoor home setting and suitable for small spaces.

Sport sessions will be delivered by a Physical Activity Instructor with experience running physical activity/sport programs for youth with ID and familiar with instructional, motivational, and behavior modification strategies appropriate for this population. The Instructor will also have some experience delivering physical activity programs remotely. The Instructor will lead and demonstrate all activities in the session and provide verbal instruction, prompting, corrective feedback, and encouragement to engage participants in the activities using proper form. The Research Assistant (RA) will assist the Instructor during the remote sessions to help keep participants on task.

The first 5 minutes of each session will be an interactive greeting to introduce participants to the sport skills of the day, to highlight having fun and trying one's best, and to gather the equipment needed for the activities. A 10-minute dynamic warm-up will prepare and engage participants for the skill circuit. These 10 minutes will focus on “footwork for sports and games” and include fundamental movement skills (e.g., running, skipping, hopping, jumping, sideways sliding) designed to engage participants and build excitement. The footwork activities will use equipment to add interest for participants. For 20 minutes, participants will engage in age- and developmentally-appropriate activities designed to foster movement proficiency through a series of 5-7 sport skill activities for 2-3 minutes each with a short rest/transition between each one. Activities will include catching, throwing, kicking, striking with a paddle, juggling, foot dribbling, and jumping, jogging, and hopping in place using equipment. To increase enthusiasm and engagement, we will include individual, partner, and group challenges with many of the activities.

As originally proposed, the sport skills program will include an additional opportunity for skill development via an at-home play/practice component. Participants will be encouraged to use the equipment from their kit to practice skills outside of the session. We will create activity cards and videos with simple and fun ideas for playing with the equipment both indoors and outdoors. The cards and videos will contain instructions, pictures, and motivational cues to encourage participants to practice kicking, dribbling, throwing, catching, jumping, etc. The goal of the practice is to have participants enjoy sports/physical activities in an unstructured way and to

provide greater exposure. Each session, the Instructor will ask participants if they practiced and to share their experiences. This will be a positive interaction with reinforcement, encouragement, and strategies for practicing skills at home if youth report challenges. As before, we will ask participants to record their participation and submit it to us, but instead of paper-based recording, we will use an online reporting tool through REDCap. Participants will be reminded to input their at-home practice into REDCap using an automated text messaging and emailing application called Remind.

**Healthy Eating.** After a brief break, youth and parents will meet with the Nutrition Educator after the sport sampling portion of the program. In general, nutrition sessions will focus on a simple nutrition messages, and will include demonstrations, brief interactive activities, some food preparation, and a taste test. In our experience, these sessions are best done in 30-minute blocks.

We previously developed modules around healthy eating for adolescents with ID, *Health U: A Nutrition Curriculum for Teenagers with Intellectual & Developmental Disabilities* ([www.tinyurl.com/HealthUCurriculum](http://www.tinyurl.com/HealthUCurriculum)) that uses hands-on activities to teach about healthy eating. We have implemented these sessions in our weight management interventions and nutrition education programs for youth with ID. We are adapting and building on this curriculum for remote delivery. The program will begin with an introduction, followed by sessions focusing on how to incorporate foods from each food group into meals/snacks using “MyPlate” ([www.choosemyplate.gov](http://www.choosemyplate.gov)). The 12 modules include the following topics: 1) Introduction to the nutrition education component of the program; 2) Learn about MyPlate and food groups; 3) Fruits; 4) Vegetables; 5) Dairy; 6) Whole grains; 7) Proteins; 8) Putting a healthy meal together; 9) Added sugars; 10) Healthy snacks; 11) Promoting healthy snacks with fruits and vegetables; and 12) Planning a meal. Healthy eating principles will be reflected in the activities and we will regularly review previously covered material, as youth with ID need repetition and review to promote knowledge retention and skill development. Parents and youth will participate together in the sessions.

Each session will begin with an introduction of the topic, followed by an activity and a taste test. Taste tests will be thematically related to the lesson and participants will help with basic food preparation, learning the skills of assembling and spreading to prepare snacks, such as yogurt and fruit smoothies. We will ask participants to rate the food as: “*I like it*”; “*I don’t like it*”; “*I didn’t try it*”; and “*Maybe I will try it next time*” using a rating sheet that includes words and pictures (emoticons).

Each week the Nutrition Educator will start the session by asking the youth whether they tried a new food the previous week and what they thought about it. They will then engage the group in a brief review of the previous week’s topic. Next the Nutrition Educator will provide a brief review of the current week’s topic, after which youth and parents will be assigned to Zoom breakout rooms with 2-3 other parent/youth dyads. In each break-out room a nutrition student will lead an activity related to the topic. In some lessons, the group will remain together.

Health Eating activity materials will be sent to the participants’ homes three times throughout the intervention. We will provide the food to families for the weekly sessions by way of a direct grocery delivery, if feasible, or by providing them with the financial resources to make the

purchases themselves. The taste test foods will not require any cooking or heating to help minimize the time away from the group, as well as parental burden.

We will apply the at-home practice concept of “*Give it a try*” to the healthy food component of the intervention as with the sport sampling. Youth will record any new foods they tried over the week using a simple online form through REDCap. At the beginning of each session the instructor will ask the youth to report any new foods they tried during the week as a way to engage them in discussion and help motivate them to try new foods.

